Talimogene Laherparepvec Cycle		1	1	1	2	2	2	3	4	5	6	7	8	9	10	11	12	13	14	15	16			
Day		1	2	8	22	23	29	36	50	64	78	92	106	120	134	148	162	176	190	204	218			
Radiographic Tumor/Response Assessments^d																								
Radiographic scans (± 7 days; appropriate to tumor) ^e	X								X				X							X		X	X ^f	
Clinical tumor assessment ^{h,i}	X								X				X							X		X	X	
Tumor markers (if clinically applicable) ^y	X	To be performed to confirm a suspected complete response, if elevated at baseline																			X	X		
Treatment Administration																								
Talimogene laherparepvec administration		X			X			X	X	X	X	X	X	X	X	X	X	X	X	X	X	X ^w		
Reporting Exposure to Talimogene Laherparepvec																								
Exposure of subject's household member or caregiver ^d		X	X	X	X	X	X	X	X	X	X	X	X	X	X	X	X	X	X	X	X	X	X	
Exposure of subject's healthcare provider ^{x, d}		X	X	X	X	X	X	X	X	X	X	X	X	X	X	X	X	X	X	X	X	X	X	

Approved

Footnotes defined on next page.

ECG = electrocardiogram; HSV = herpes simplex virus; qPCR = real-time polymerase chain reaction; aPTT = activated partial thromboplastin time; CR = complete response; INR = international normalization ratio; irRC-RECIST = immune-related response criteria simulating Response Evaluation Criteria in Solid Tumors; PT = prothrombin time; PTT = partial thromboplastin time; [REDACTED]; ULN = upper limit of normal

^a Treatment visits continue until the subject has achieved a complete response, all injectable tumors have disappeared, confirmed progressive disease per modified irRC-RECIST, intolerance of study treatment, 24 months from the date of the first dose of talimogene laherparepvec, or need for alternative anticancer therapy, whichever occurs first.

^b Approximately 30 (+ 7) days after the last dose of study treatment.

^c Subjects will be followed for survival and use of subsequent anticancer therapies every 12 weeks (\pm 28 days) from the safety follow-up visit until death, subject or legally acceptable representative withdraws full consent/assent, or up to approximately 24 months after the last subject is enrolled in the study, whichever occurs first.

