^s Radiologic imaging of all sites of disease must be performed (including imaging of the brain when clinically indicated). For subjects remaining on treatment with talimogene laherparepvec beyond week 32, radiologic imaging should continue every 12 weeks until confirmed progressive disease per modified irRC-RECIST or start of new anticancer treatment. All study imaging should be performed according to the calendar and not adjusted for any cycle initiation delays.

^t Subjects who are in complete response and no longer have injectable lesions will enter the 30-day safety follow-up and continue to have tumor assessments every 12 weeks for up to 24 months.

^u For subjects with metastatic melanoma, clinical tumor assessments, including clinical measurements of cutaneous, subcutaneous, or nodal measurement by caliper should be measured at baseline assessment, as well as subsequent scheduled tumor assessments. Measurements should continue every 12 weeks until confirmed progressive disease per modified irRC-RECIST or start of new anticancer treatment.

^v Clinically applicable tumor markers appropriate for the tumor type include, but are not limited to, serum alpha fetoprotein, serum beta human chorionic gonadotropin and urine for homovanillic acid/vanillylmandelic acid. Tumor marker measurement is required to confirm CR if screening level of tumor marker was above the ULN and criteria for CR per modified irRC-RECIST guidelines are met.

^w Treatment may continue for up to 24 months depending on response to and tolerance of talimogene laherparepvec.

^x If applicable.

Approved

Refer to the applicable supplemental (eg, laboratory, imaging) manuals for detailed collection and handling procedures.

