7.2.2 Treatment

Treatment begins when the first dose of protocol-required therapy is administered to a subject. Study treatment should begin as soon as possible after enrollment via the **IRT** system but no later than 5 days after enrollment.

Administration of protocol-required therapies is to be performed after all other required procedures are completed during each visit, unless otherwise stated. Upon permanent discontinuation from study treatment for any reason, a safety follow-up visit will be performed approximately 30 (+ 7) days after the last dose of talimogene laherparepvec. The time points for the procedures to be completed during the treatment period are designated in the Schedule of Assessments ([Table 3](#)).

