^b Disappearance of all non-lymph node lesions and all lymph nodes < 10 mm in short axis would also be CR even if lymph node measurements prevent 100% tumor burden reduction.

^c No non-target lesions identified at baseline.

^d Assuming response (CR or PR) or progression are confirmed by a second, consecutive assessment at least 4 weeks (28 days) apart.

^e In addition to relative increase of ≥ 20%, the tumor burden must also demonstrate an absolute increase of ≥ 5 mm from nadir for PD.

^f No target lesions identified at baseline. When a subject has only nonmeasurable disease (ie, no target lesions identified at baseline) the response will be (UE) unevaluable.

^g If one or more target/new measurable lesions are unevaluable or not measured but the sum of all evaluable target/new lesions measured show a ≥ 20% and at least 5 mm absolute increase relative to nadir, then the visit overall Target Response will be PD.

Determination of best overall response is based on changes in total tumor burden from the baseline (nadir, for PD) tumor assessment, regardless of any initial increase in baseline lesions or the appearance of new lesions.

Subjects are considered to have partial response (PR) or stable disease (SD) even if new lesions were present, as long as they met the respective thresholds of response as described in [Table 7](#).

A best overall response of SD requires a visit response of SD or better no earlier than 49 days after the date of enrollment; otherwise the overall response will be UE.

Approved

Confirmation of Response (CR or PR):

To be assigned a status of CR or PR changes in tumor measurements must be confirmed by consecutive repeat assessments performed no less than 4 weeks (28 days) after the criteria for response are first met.

In some circumstances it may be difficult to distinguish residual disease from normal tissue. When the evaluation of CR depends on this determination, it is recommended that the residual lesion be investigated (ie, biopsy) to confirm the CR status.

Confirmation of Disease Progression:

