### Best overall response (BOR) per Modified irRC-RECIST

Best overall response (BOR) of complete response (CR), partial response (PR), stable disease (SD), progressive disease (PD) or un-evaluable (UE) will be derived based on

investigator assessment using modified irRC-RECIST as defined in protocol Appendix D. Any baseline tumor markers above the ULN must normalize for an overall visit response of CR.

Overall visit response assessments occurring after the start of the first subsequent anticancer therapy, including complete or partial removal/reduction of any target lesion, will not be included. Consecutive confirmation of CR, PR, and PD is required where the second overall response must be at least 28 days from the first, the only exception being when the investigator reports that an initial PD cannot be confirmed due to rapid clinical deterioration. The following will be considered a confirmed PR: CR followed by PR or PR followed by CR.

BOR is defined as the best visit response in the following order: CR, PR, SD, PD, or UE (see [Table 3](#)). BOR is defined as SD if the best overall visit response is an unconfirmed CR or PR, and UE if it is either SD earlier than 49 days after the date of first dosing or an unconfirmed PD when confirmation of PD is required (ie, initial PD without rapid clinical deterioration).

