**Table 3. Matrix of Determining BOR per Modified irRC-RECIST**

Visit Overall Response Sequence	Examples	Best Overall Response	Confirmation specifications
* , CR, CR, *	PR, CR, CR CR, CR, PD	CR	The confirmatory CR must be at least 4 weeks (28 days) later; a subsequent CR within 28 days will not be valid for confirmation and will be ignored; the CR will also not be confirmed if there is a subsequent PR/SD/PD at any time prior to the next CR.
* , PR, PR, *  * , PR, CR/PR, non-CR, *  * , CR, PR, *	PR, PR, PD PR, CR, PD  CR, PR, PD	PR	Criteria for BOR=CR not met. The confirmatory PR/CR must be no less than 4 weeks (28 days) later; a subsequent PR/CR within 28 days will not be valid for confirmation and will be ignored; the PR will also not be confirmed if there is a subsequent SD/PD at any time prior to the next PR/CR .
* , SD, *  * , CR, non-PR/CR, *  * , PR, non-PR/CR, *	CR PD, CR PR PD, PR, SD SD PD,SD,PD	SD	Criteria for BOR=CR or PR not met. SD must be $\geq$ 49 days from first dose; however, this is not required for an unconfirmed CR/PR.

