**Study day**

Study day is calculated from the first day when investigational product is administered to the subject.

That is, Study day = visit date – first dose date + 1, if visit date is after first dose date

Study Day = first dose date – visit date, if visit date is prior to first dose date

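### The SAP's 49-day minimum for stable disease falls on the nominal first scan day, leaving no room for the early half of the ±7-day window, and it runs from a different date than the protocol's

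*SAP*

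**What the plan says.** **SAP, Section 6 (Best overall response) and Table 3.** BOR is to follow the modified irRC-RECIST criteria in protocol Appendix D. It is set to UE if the best visit response is "SD earlier than 49 days after the date of first dosing". SAP Table 3 repeats the minimum, counted from first dose. For an unconfirmed complete or partial response (CR/PR) it adds: "however, this is not required for an unconfirmed CR/PR". The UE row of the same table also mentions randomization, although this is a single-arm study.

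**Protocol, Appendix D.** A BOR of SD "requires a visit response of SD or better no earlier than 49 days after the date of enrollment"; otherwise it is UE.

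**Protocol, Table 3 (Schedule of Assessments).** The scan row is labelled "Radiographic scans (± 7 days; appropriate to tumor"), and its first on-treatment mark is in the Day 50 / Week 8 column. A footnote fixes the timing: "All study imaging should be performed according to the calendar and not adjusted for any cycle initiation delays".

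**Protocol, Section 7.2.2.** Treatment must start "no later than 5 days after enrollment".

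**SAP, Section 11.** The only declared departure from the protocol concerns the DLT analysis set.

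**The concern.** A minimum time for SD is meant to stop a very early scan from counting as disease stability. It should not reject the first scan that the schedule itself calls for. Here the minimum equals the nominal day of that scan, so a site that images a few days early but within the window produces an SD that the SAP will not accept. The next scheduled on-treatment scan is in the Day 106 column, so for some subjects the first scan may be the only one able to support SD.

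The two documents also start the same 49 days from different dates. One subject can then have two BOR values, depending on which document the programmer follows. At stake is how subjects are divided among SD, UE and PD in a trial of 18 to 24 dosed subjects.

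**Working it through.** **Inputs**

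- SD minimum: 49 days, from first dose (SAP Section 6 and Table 3) or from enrollment (protocol Appendix D).
- First on-treatment scan: Day 50 (protocol Table 3, by column position). The physical-examination row supports the alignment. Its marks fall on Days 1, 50, 106, 162 and 218, and from Day 50 they are 56 days apart, which is four 14-day cycles and matches the every-fourth-cycle footnote.
- Scan window: ±7 days (protocol Table 3).
- Day count: "Study day = visit date – first dose date + 1" (SAP Section 6).
- Lag *L* from enrollment to first dose: 0 to 5 days (protocol Section 7.2.2).

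**Step 1. Nominal scan.** Days after first dose = study day − 1. For Day 50 this is 50 − 1 = 49, exactly the minimum.

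**Step 2. Window.** 50 − 7 = 43 and 50 + 7 = 57, so Days 43 to 57 are permitted. That is 15 days, or 42 to 56 days after first dose.

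**Step 3. SAP rule.** A scan fails if (study day − 1) < 49. Days 43 to 49 fail (42 to 48 days after first dose): 7 of 15 permitted days, 47%.

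**Step 4. Protocol rule.** A scan fails if (study day − 1 + *L*) < 49.

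| Lag *L* (days) | Days failing the protocol rule | Days passing the protocol but failing the SAP |
|---|---|---|
| 0 | 43–49 | none |
| 1 | 43–48 | 49 |
| 2 | 43–47 | 48–49 |
| 3 | 43–46 | 47–49 |
| 4 | 43–45 | 46–49 |
| 5 | 43–44 | 45–49 |

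Example: first dose 5 days after enrollment, SD scan on Day 45. The scan is 44 days after first dose, so it fails in the SAP. It is 44 + 5 = 49 days after enrollment, so it qualifies in the protocol.

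**Step 5. What happens to BOR.** The visit response stays SD. Under SAP Table 3:

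- a later SD at 49 days or more restores SD;
- any CR or PR, even unconfirmed, gives SD or better;
- otherwise, confirmed PD or PD with rapid clinical deterioration gives PD;
- otherwise, including SD followed by an unconfirmed PD, BOR is UE.

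**Step 6. Other endpoints.** ORR counts only CR and PR, and DOR and TTR concern responders. TTP and PFS censor at the last evaluable assessment, which the SAP defines by visit response, so the early SD scan still counts there. OS does not use tumor assessments. None of the six changes.

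**Step 7. Weight of one subject.** If all dosed subjects are in the denominator, one relabelled subject moves the SD share by 1/24 = 4.2 to 1/18 = 5.6 percentage points. It moves more if subjects without baseline measurable disease are excluded.

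**Step 8. Effect of the change.** 49 − 7 = 42 days. Day 43 is 42 days after first dose and passes, so 0 of 15 permitted days fail.

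**The case against.** **The 49 days may already contain the window.** The visit is labelled Week 8, and 8 weeks less 7 days is 56 − 7 = 49. This does not stand. The SAP makes Day 1 the first day of Week 1, so Week 8 begins on Day (8 − 1) × 7 + 1 = 50, which is 49 days after first dose, not 56. The schedule itself prints Day 50 under Week 8.

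**Later scans limit the harm.** This stands in part. The schedule has scans in the Day 106 column and at the safety follow-up visit, and protocol Section 7.2.3.2 asks for 12-weekly scans after treatment stops for reasons other than confirmed PD. A later SD restores the category. A later PD does not, so subjects whose next scan shows progression remain exposed.

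**No listed endpoint depends on it.** This is correct. The visible secondary endpoints include neither an SD rate nor a disease control rate.

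**A stricter minimum is a legitimate convention.** It can be, but neither document says that compliant scans on Days 43 to 49 are to be excluded on purpose.

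**Stronger readings that the documents do not support.** A reader might take 47% as the share of subjects misclassified. It is a share of permitted days, and would forecast early scans only if scan days were spread evenly over the window; even then, BOR changes only for subjects with nothing later to rescue it. A reader might also infer that the documents conflict for scans on both sides of the SAP cut. They cannot, because enrollment never follows first dose: a scan at 49 days or more from first dose meets both rules. Nor do the documents show that rapid progression makes the problem common.

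**Conclusion.** The point holds as a defect in one analysis definition. A protocol-compliant SD scan on Days 43 to 49 cannot support a BOR of SD under the SAP, and for scans on Days 45 to 49 the protocol and SAP can disagree, depending on the lag to first dose. The change of starting date is undeclared. The number of subjects affected cannot be estimated from the documents. It is limited to those with an early first SD scan, no later SD at 49 days or more, and no CR or PR.

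The conclusion rests on Day 50 as the first scan, read from column position in a table extracted from PDF. It also takes 49 days after first dose as elapsed days, as the wording implies. If the rule were programmed as study day 49, Days 43 to 48 would fail (6 of 15) and the conclusion would be the same. The matter merits correction but does not threaten the primary endpoint or the listed secondary endpoints.

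**What to change.** In SAP Section 6 and SAP Table 3:

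- set the minimum for a BOR of SD at 42 days from first dose, being the first scheduled scan at 49 days less its 7-day window;
- remove the mention of randomization from the UE row;
- list both the starting date and the new minimum in Section 11 as changes from the protocol.

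First dose is the natural starting point because the SAP already uses it for TTR, TTP, PFS and OS. Appendix D should be aligned at the next protocol amendment. That amendment should also settle whether an unconfirmed CR/PR is exempt from the minimum, since the SAP exempts it and Appendix D does not.

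The SAP edit is small. The Appendix D edit is a protocol amendment, needing investigator agreement and ethics approval under protocol Section 12.1, so it need not be made on its own. The analytic cost is that SD can be assigned up to one week earlier. The change also comes mid-study in an open-label trial; Amendment 3 reports 11 subjects already enrolled. It should therefore be documented before the primary analysis, with BOR under the 49-day rule shown as a sensitivity tabulation.

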**Table 3. Matrix of Determining BOR per Modified irRC-RECIST**

Visit Overall Response Sequence	Examples	Best Overall Response	Confirmation specifications
* , CR, CR, *	PR, CR, CR CR, CR, PD	CR	The confirmatory CR must be at least 4 weeks (28 days) later; a subsequent CR within 28 days will not be valid for confirmation and will be ignored; the CR will also not be confirmed if there is a subsequent PR/SD/PD at any time prior to the next CR.
* , PR, PR, *  * , PR, CR/PR, non-CR, *  * , CR, PR, *	PR, PR, PD PR, CR, PD  CR, PR, PD	PR	Criteria for BOR=CR not met. The confirmatory PR/CR must be no less than 4 weeks (28 days) later; a subsequent PR/CR within 28 days will not be valid for confirmation and will be ignored; the PR will also not be confirmed if there is a subsequent SD/PD at any time prior to the next PR/CR .
* , SD, *  * , CR, non-PR/CR, *  * , PR, non-PR/CR, *	CR PD, CR PR PD, PR, SD SD PD,SD,PD	SD	Criteria for BOR=CR or PR not met. SD must be $\geq$ 49 days from first dose; however, this is not required for an unconfirmed CR/PR.

**Table 3. Matrix of Determining BOR per Modified irRC-RECIST**

Visit Overall Response Sequence	Examples		Best Overall Response	Confirmation specifications
* , PD, PD, *  * , PDr, *  PDr = PD with concurrent or subsequent rapid clinical deterioration as the reason for ending radiographic follow-up.	PD, PD PD, SD, PD, PD PDr		PD	Criteria for BOR= CR, PR, or SD not met. The confirmatory PD must be no less than 4 weeks (28 days) later unless there is rapid clinical deterioration; PDr does not require confirmation; a subsequent PD within 28 days will not be valid for confirmation and will be ignored.
* , SD, *  PD	SD UE, SD PD UE, PD		UE	Criteria for BOR=CR, PR, SD, or PD not met. SD must be < 49 days from first dose (or randomization if not treated).

Page 2 of 2

**Duration of response (DOR) per Modified irRC-RECIST**

Duration of response (DOR) is defined as the time from the date of an initial response that is subsequently confirmed to the earlier of PD (see definition of BOR per Modified irRC-RECIST) or death. Subjects who have not ended their response at the time of analysis will be censored at their last evaluable tumor assessment.

**Evaluable tumor assessment**

[figure not shown]
An overall visit response other than UE.

[figure not shown]
**Event of Interest (EOI)**

MedDRA dictionary preferred terms for each EOI search strategy is defined and maintained by Amgen Safety Medical Coding.

**Investigational product (IP)**

Investigational product refers to talimogene laherparepvec in this study.

**Objective response rate (ORR) per Modified irRC-RECIST**

[figure not shown]
ORR is defined as the incidence of a BOR of CR or PR per Modified irRC-RECIST among a set of subjects analyzed. Subjects who do not have any follow-up tumor assessments will be regarded as non-responders.

**Overall Survival (OS)**

OS is defined as the interval from first dose to the event of death from any cause; otherwise, OS is censored at the date the subject was last known to be alive.

[figure not shown]
**Potential Follow-Up Time**

Potential follow-up time for a subject is calculated from the first dose to the analysis data cutoff date.

**Progression-free survival (PFS) per Modified irRC-RECIST**

Progression-free survival (PFS) per Modified irRC-RECIST is defined as the interval from first dose to the earlier of PD per Modified irRC-RECIST or death from any cause; otherwise, PFS is censored at the last evaluable tumor assessment. The initial date of PD will be the PFS date when it is consecutively confirmed.

**Study day**

Study day is calculated from the first day when investigational product is administered to the subject.

That is, Study day = visit date – first dose date + 1, if visit date is after first dose date

Study Day = first dose date – visit date, if visit date is prior to first dose date

**Study Day 1**

Study day 1 is defined as the first day of administration of the investigational product after enrollment. The day prior to Study Day 1 is considered Study Day -1.

**Study Week 1**

The start of Investigational product administration to the subject is study week 1. Study day 1 is corresponding to the first day of study week 1.

**Time to progression (TTP):** defined as the interval from first dose to the date of the first PD per Modified irRC-RECIST; otherwise, TTP is censored at the last evaluable tumor assessment.

**Time to response (TTR):** (calculated only for those subjects in the safety analysis set with confirmed CR or PR) time from first dose to the date of the first confirmed CR or PR.

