10.4.2 Secondary Endpoints

Efficacy Endpoints:

ORR, DOR, TTR, TTP, PFS, and OS will be summarized in the overall population. ORR will be summarized with an associated exact 95% CI using the safety analysis set and excluding subjects without baseline measurable disease, if applicable. DOR among responders, TTR, TTP, PFS and OS will be estimated using the Kaplan-Meier method.

Safety Endpoints

Subject incidence of treatment-emergent and treatment-related adverse events will be summarized. **Treatment-emergent adverse events are defined as any adverse event occurring after first dose through 30 days after last dose of talimogene**

laherparepvec. Treatment-related adverse events are defined as treatment-emergent adverse events which are considered to be related to the treatment of talimogene laherparepvec, as determined by the investigator. Medical Dictionary for Regulatory Activities (MedDRA) will be used to code adverse events to a system organ class (SOC) and a preferred term within the SOC. The CTCAE version 4.0 will be used to grade severity of adverse events. In addition, clinically significant laboratory changes and clinically significant changes in vital signs will be summarized with descriptive statistics.

Subject incidence of all disease-related events, fatal disease-related events, serious disease-related events, and disease-related events leading to withdrawal from study drug will be provided.

[figure not shown]
A summary of deaths after initiation of the study through 30 days since the last dose of talimogene laherparepvec will be provided.

Summary statistics will also be provided for concomitant medications, dose delay, study drug discontinuation, overall exposure, and Karnofsky performance status and Lansky play scale.

[figure not shown]
Potential or known unintended exposure to talimogene laherparepvec, related suspected signs or symptoms, and detection of exposure to talimogene laherparepvec in a subject's household member, caregiver, or healthcare provider will be reported.

Summary statistics will be provided for vital signs, physical measurements and laboratory data. Details of the analysis will be provided in statistical analysis plan.

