## 10. Statistical Methods of Analysis

### 10.1 General Principles

The DLT Analysis Set will be used to summarize the subject incidence of DLT and the Safety Analysis Set will be used for all other analyses of safety and efficacy endpoints.

Descriptive statistics will be provided for efficacy, safety, talimogene laherparepvec DNA, and other exploratory endpoints for all subjects and by cohort. Summary statistics including mean, standard deviation, median, first and third quartiles, minimum and maximum will be provided for continuous variables. Frequency and percentage will be summarized for binary and categorical variables. Proportions and the corresponding exact 95% confidence intervals using F distributions will be calculated (Clopper & Pearson 1934). Exact tests will be considered for subgroup analyses. Time to-event endpoints will be estimated using the K-M method.

Separate reporting at a program-level may occur of close contact and HCP events with or without a known unintended exposure.

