#### 10.5.1 Analyses of Secondary Endpoints - ORR, DOR, TTR, TTP, PFS, OS

[figure not shown]
Analysis of secondary endpoints such as ORR, DOR, TTR, TTP, PFS, OS will be based on Safety Analysis Set and excluding subjects without baseline measurable disease, if applicable.

- ORR (CR+PR) will be summarized with associated exact 95% CIs for binomial proportions (Clopper & Pearson 1934).

- DOR among responders, TTP, PFS and OS will be estimated using the Kaplan-Meier method and estimates of event time quartiles, event-free rates at selected times and the corresponding 95% CIs will be provided.
- Summary statistics will be estimated for TTR among responders.

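### TTP is estimated by Kaplan-Meier with deaths without PD censored, so 1 minus the curve overstates documented progression if others progress after such a death; add a cumulative-incidence estimate

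*SAP*

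**What the plan says.** SAP Section 6 (Definitions) has TTP "defined as the interval from first dose to the date of the first PD per Modified irRC-RECIST" and continues: "otherwise, TTP is censored at the last evaluable tumor assessment". Death is not mentioned, so a subject who dies without PD falls under the censoring rule. The neighbouring definitions differ. PFS runs from "first dose to the earlier of PD per Modified irRC-RECIST or death from any cause", and DOR also ends at the earlier of PD or death.

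For estimation, SAP Section 10.5.1 states "DOR among responders, TTP, PFS and OS will be estimated using the Kaplan-Meier method and estimates of event time quartiles, event-free rates at selected times", with 95% confidence intervals. Protocol Section 10.4.2 names the same method ("DOR among responders, TTR, TTP, PFS and OS will be estimated using the Kaplan-Meier method"), and SAP Section 10.1 gives it as the general rule: "Time to-event endpoints will be estimated using the K-M method". Neither document names a competing-risk method or says how the TTP curve is to be read when subjects die without PD.

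**The concern.** Death without PD makes later PD impossible. Censoring treats that subject as someone who could still progress, and Kaplan-Meier passes the subject's weight to those who progress later. The resulting event-free rate describes a setting in which nobody dies before progressing. A reader of the study report is likely to take its complement as the share of treated subjects who progressed, and that share would be too high.

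PFS, reported beside TTP, counts these deaths but does not correct the quartiles and event-free rates printed for TTP. With 18 to 24 dosed subjects, a few such deaths can visibly move the curve. What is at stake is how one descriptive secondary endpoint is read. The DLT endpoint and the dose decisions do not use TTP.

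**Working it through.** **Figure to reproduce.** None. The documents state no TTP rate, progression share or death rate.

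**Inputs from the documents.** PD is the only TTP event, and all other subjects are censored at the last evaluable assessment (SAP Section 6). Kaplan-Meier is the estimator (SAP Section 10.5.1). The study has 18 to 24 dosed subjects (SAP Section 3.2).

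**Assumed inputs.** F is the probability of PD or death by time t. q is the share of first events that are deaths without PD. Cause-specific hazards are constant.

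**Step 1: hand example, 18 subjects.** Six have PD at week 12. Three die before week 24 and are censored at week 12. Five have PD at week 24.
- 1-KM = 1 - (12/18) x (4/9) = 70.4%.
- Documented PD = 11/18 = 61.1%. The excess is 9.3 points.
- PD or death = 14/18 = 77.8%.
- With one such death instead of three: 1 - (12/18) x (6/11) = 63.6% against 61.1%, an excess of 2.5 points.
- With none: 1 - (12/18) x (7/12) = 61.1% both ways.

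**Step 2: closed form.** Cumulative incidence of PD = F(1-q), and 1-KM = 1-(1-F)^(1-q). For F = 80% and q = 20%: 0.80 x 0.80 = 64.0%, against 1-0.20^0.80 = 72.4%, a difference of 8.4 points. Each cell gives the cumulative incidence, then 1-KM, then the difference in points.

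| F | q = 5% | q = 10% | q = 20% | q = 30% |
|---|---|---|---|---|
| 60% | 57.0 / 58.1 / +1.1 | 54.0 / 56.2 / +2.2 | 48.0 / 52.0 / +4.0 | 42.0 / 47.3 / +5.3 |
| 80% | 76.0 / 78.3 / +2.3 | 72.0 / 76.5 / +4.5 | 64.0 / 72.4 / +8.4 | 56.0 / 67.6 / +11.6 |
| 90% | 85.5 / 88.8 / +3.3 | 81.0 / 87.4 / +6.4 | 72.0 / 84.2 / +12.2 | 63.0 / 80.0 / +17.0 |

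**Step 3: simulation with the planned type of censoring.** There were 3,000 trials per scenario, with a 52-week horizon and deaths censored at the last scan. Scans were every 12 weeks throughout. The protocol states that interval for treatment beyond week 32, so its use for the whole period is an assumption. Excess of 1-KM over the documented PD share, N = 18:

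| F | q = 5% | q = 10% | q = 20% | q = 30% |
|---|---|---|---|---|
| 60% | +1.3 | +2.5 | +4.5 | +5.9 |
| 80% | +2.8 | +5.5 | +10.0 | +13.6 |
| 90% | +4.3 | +8.4 | +15.1 | +21.1 |

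N = 24 gives the same values to within 0.3 points. Censoring at the last scan does not remove the effect.

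**Step 4: medians.** With Kaplan-Meier median m and hazard of any first event h = ln2/[m(1-q)], the cumulative incidence reaches 50% where (1-q)(1-exp(-ht)) = 0.5. For q = 10, 20 and 30%, a 3-month Kaplan-Meier median becomes 3.2, 3.4 and 3.8 months. A 6-month median becomes 6.3, 6.8 and 7.6 months. The largest shift is 1.6 months.

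**Step 5: direction.** If all three deaths in Step 1 were progression that no scan recorded, clinical progression would be 14/18 = 77.8%. Then 1-KM (70.4%) is too low by 7.4 points, and the cumulative incidence of documented PD (61.1%) is lower still.

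**The case against.** **The plan limits deaths without PD.** A reader might infer from the entry criterion of more than 4 months' life expectancy and the widely spaced scans that such deaths are likely. The documents do not support that.
- The life-expectancy criterion is a floor that screens out early deaths. The schedule of assessments appears to place the first two on-treatment scans at Day 50 and Day 106, both within about 4 months.
- Confirmation of PD is waived in one case, "the only exception being when the investigator reports that an initial PD cannot be confirmed due to rapid clinical deterioration", so a PD scan followed by rapid decline counts as PD.
- Protocol Section 7.2.3.2 asks for scans every 12 weeks after treatment stops for reasons other than confirmed PD. Appendix D asks for every effort to document progression after discontinuation.

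This stands. Such deaths remain possible, for example between scans or before a required confirmation, but their frequency is unknown.

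**Large shifts come from uninformative time points.** One can obtain shifts of 8, 16 and 25 points at 12 months by assuming a 3-month Kaplan-Meier median and 10, 20 and 30% dying first. With n = 18, the expected number still at risk at that point is 18 x exp(-12h) = 0.83, 0.56 and 0.34 subjects. With a 6-month median read at 6 months, the shifts are 1.7, 3.6 and 6.0 points. The SAP does not commit to 12 months for TTP. This also stands.

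**The definition is conventional.** Censoring deaths is a common TTP definition, and PFS and OS are reported in the same section. No test or decision rule uses TTP. This argues for keeping the Kaplan-Meier TTP and for a low priority. It does not correct the TTP figures themselves or show how many deaths were censored.

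**Conclusion.** The point holds in a limited form. As written, 1-KM for TTP is never below the cumulative incidence of documented PD, and it is above it once a PD follows a censored death. The excess is zero with no such deaths, about 1 to 4 points if 5% of first events are deaths without PD, and about 5 to 21 points if 30% are. Medians shift by less than about 2 months. These sizes rest on constant hazards and on an assumed 60 to 90% chance of PD or death by one year. None of these rates comes from the documents.

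Two stronger readings should be avoided. A reader might conclude that TTP overstates progression in general. The direction holds only for documented PD, and it can reverse for clinical progression if some deaths are progression that was missed or not confirmed. A reader might also conclude that the Kaplan-Meier TTP is an error to be replaced. It is a conventional summary, of a hypothetical setting without deaths, that needs a label and a companion estimate. This is a cheap, optional improvement to a descriptive secondary endpoint.

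**What to change.** In SAP Section 10.5.1, add the cumulative incidence of PD (Aalen-Johansen estimator), with death without prior PD as a competing event. Report the number and the cumulative incidence of deaths without PD beside it. Keep the Kaplan-Meier TTP for comparability with other trials, and label it as treating deaths without PD as censored. Leave PFS unchanged. List the addition in SAP Section 11.

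The PD and death dates are already needed for PFS and OS, and the estimator is in standard software. If the same event and censoring dates are used as for PFS, the two cumulative incidences add up to 1 minus the Kaplan-Meier PFS estimate, which gives a simple programming check.

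The cost is a few sentences in the SAP and one extra descriptive output. Its intervals will be very wide at 18 to 24 subjects, and it does not settle whether a death without PD was unrecorded progression.
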